During cesarean delivery: Surgery, intraoperative and postoperative management will be performed according to standard practice. Data will be collected on heart rate, blood pressure, oxygen saturation, presence of nausea and vomiting and use of wound infiltration. Acute pain in the postoperative care unit (PACU) will be treated at clinician's discretion.

After delivery and before discharge from the hospital: The woman is interviewed at 0 to 48 hours on the pain scores at rest and with movement (sitting up in bed from a supine position) and will be recorded in the nursing electronic records. Other data such as nausea scores, and occurrence of vomiting are also noted. Standard routine monitoring of haemodynamics parameters and pain relief will be done in the ward. Study surveys are continued while patient is comfortable before discharge or till 5-14 days after discharge. The survey for post-delivery health status (HADS, EQ-5D-3L) will take about 10 minutes to complete.

Six - Ten weeks after delivery: The patient will have a phone survey/ online survey at 6 -10 weeks post-delivery with: (1) EPDS (2) Pain Survey (3) Pain Vulnerability (PCS, CSI) (4) Breastfeeding Questionnaire (5) EQ-5D-3L and (6) HADS. Patients with scores on the depression scale consistent with postpartum depression will be referred to their obstetrician or primary care physician for further assessment and management.

F9. Please provide details on sample size and power calculation and the means by which data will be analyzed and interpreted (if applicable).

As an observational study, we will target to enrol for up to 200 consented subjects. The primary hypothesis will be assessed with a Pearson correlation test at $\alpha=0.05$ cutoff for statistical significance. The secondary numeric measures of pain, nausea, and satisfaction will be assessed for correlation with the preoperative measures using a Pearson correlation test. Anticipating that some patients will not require rescue oxycodone, we plan to analyze the time to rescue oxycodone via Kaplan-Meier mean time to event analysis. Dichotomous variables will be assessed via chi-square tests or fisher exact tests.

F10. List all activities that are carried out as part of research in this study. Please state/list all procedures involved in this research study and attach the data collection form (if any) which will be used for CIRB review.

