Analgesic choices will be made upon patient request and routine hospital protocol, monitoring and recording will apply. If subjects are screened to have high EPDS (13 or more) or persistent pain, they would be advised to seek clinical psychiatric or pain assessment at KK Hospital. The assessment would be done as clinical work and not research funded.

No new research medications are involved by joining the study. The drugs being delivered are the same as what the patient shall receive as standard care.

F14. What are the potential benefits (direct as well as indirect) to participants? Indirect benefit may refer to the medical knowledge gained in the future, from the research.

As this will be an observational study, there will be no direct benefits or harms to patients who choose to participate in this study. On a population level, the data collected in this study may help to improve pain management for women undergoing cesarean delivery in the future.

F15. What is the estimated timeline for this study?

(i) Estimated start date 01-Jun-2017

(ii) Estimated end date 01-Jun-2019

Section G: Recruitment Details

G1. How will potential participants be identified? Please tick all the applicable boxes.

NOTES:

If you have selected that participants are “Patients of study team”, please select “Yes” for K6. If healthy volunteers are recruited for the study, please select the option “Other methods of participant identification” and describe your method(s) of participant identification.

- Referral by attending healthcare professional
- Patients of study team
- Databases
- Other methods of participant identification

G2. Who will make the first contact with participant?

Investigators and the clinical research coordinators in the study team will make the first contact with participant.

G3. How will the participant be contacted?

This study will be advertised with brochures. These will be distributed through KKH, and given to all patients who meet the inclusion criteria during antenatal period. Potential study patients may be invited to participate by study team members in the antenatal clinics/wards and preoperative rooms/wards at KKH. On admission to preoperative rooms/wards, they will again be given a study brochure. The investigators and study team will be available to answer any queries on this trial in the antenatal clinics/wards and preoperative rooms/wards, through phone and email correspondence.

Recruitment of patients from antenatal clinics/wards:

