All potential patients who are expected to meet the inclusion/exclusion criteria at term and are seen in the KKH antenatal clinics/wards will be invited to participate in the study.

The informed consent process may be conducted at any time during prior to labour. Obstetricians and research team will approach the patients in the antenatal clinics/wards to provide information about the study. If a patient consents prior to labour, a copy of the consent form will be kept in the patient's case notes. The study investigator will recheck the inclusion/exclusion criteria when the patient is at the preoperative rooms/wards prior to the initiation of the study activities.

Recruitment of patients at preoperative rooms/wards:

The patients will receive the study brochure when they arrive at the preoperative rooms/wards if the patients have pain score of 3 or less (out of 10 using numerical rating scale) and not in distress. Screening for inclusion/ exclusion criteria will be performed and discussion of the study will be done by the study investigators.

G4. Will any advertising/recruitment materials be used to recruit research participants?

Yes

Brochures

Please state the location(s) where the brochures will be placed (e.g. in the general waiting area in Clinic X), and attach a copy of the brochure.

Brochures will be placed and distributed in Antenatal clinics/wards and preoperative

G5. Will any other recruitment strategies be used (e.g. talks in public places, societies etc.)? No

G6. What is the Recruitment Period (if applicable)? Please provide us with the approximate recruitment period.

Start Date: 01-Jun-2017

End Date: 01-Jun-2019

G7. How long will the participants be directly involved in the study (if applicable)? This includes the time from the screening procedures till completion of follow-up tests or examinations.

If applicable, please elaborate.

The duration of study period for each participant can last about 17 weeks. Below are the main time points for the study activities:

- Screening and recruitment time point: gestational age week 36 and above (duration: 4 weeks)
- Pain assessment and questionnaire completion time point (duration of labour till 5-14 days after discharge: ~19 days)
- Follow up phone call survey time point: 6-10 weeks after delivery (duration: 10 weeks)

Section H: Study Sites & Recruitment Targets

H1. Please state the target number of research participants to be recruited for each study site.

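### Does closing recruitment and the study on the same day, with a participant duration of about 17 weeks, leave the 6-10-week survey without time?

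*Protocol*

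**What the plan says.** F15 runs the study from 01-Jun-2017 and gives "Estimated end date 01-Jun-2019". G6, which asks for an approximate recruitment period, repeats the start date and gives "End Date: 01-Jun-2019".

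For follow-up, F8 states: "The patient will have a phone survey/ online survey at 6 -10 weeks post-delivery". F10, F11 and G7 repeat this contact.

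F10, F11 and G7 also say: "The duration of study period for each participant can last about 17 weeks". G7 explains what is counted: "This includes the time from the screening procedures till completion of follow-up tests or examinations". It then lists three components. One is a recruitment period of 4 weeks, starting at 36 weeks of gestation. Another covers the pain assessments and questionnaires around and after surgery and is put at roughly 19 days. The last is the survey: "Follow up phone call survey time point: 6-10 weeks after delivery (duration: 10 weeks".

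**The concern.** Two things look wrong. First, there are 0 days between the last recruitment and the end of the study, while the schedule needs at least six weeks after the last delivery. Recruitment may also precede delivery by about four weeks. If the end date were enforced, the latest recruits would lose the 6-10-week contact. That contact carries the follow-up EPDS, the pain survey, PCS, CSI, HADS, EQ-5D-3L and the breastfeeding questionnaire. Postpartum depression is a secondary outcome in the F1 abstract, so a named outcome would be incomplete for a block of women defined by calendar time.

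Second, the participant duration does not follow from its own components. The third component is counted from delivery, and so the roughly 19 days after surgery lie inside it. Adding the two counts those days twice. A reader who used the 17 weeks to work out when follow-up ends would get the wrong date.

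**Working it through.** **Inputs.** Study and recruitment from 01-Jun-2017 to 01-Jun-2019 (F15, G6), which is 730 days. Target 200 women (F9, H1). Windows of 4 weeks, about 19 days and 10 weeks (F10, F11, G7). Survey due 6 to 10 weeks after delivery (F8).

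**1. The plan's own duration.** Added end to end:

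4 + 19/7 + 10 = 4 + 2.7 + 10 = 16.7 weeks, or about 17.

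This reproduces the stated figure. The protocol does not show its sum, so double counting is an inference, but a strong one.

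**2. Duration without the overlap.** With the last window counted from delivery:

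4 + 10 = 14 weeks, which is 17 − 14 = 3 weeks less than stated.

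**3. Calendar.** 01-Jun-2019 minus 42 days is 20-Apr-2019. A woman delivering after that date reaches week 6 after the stated study end. A woman delivering on 01-Jun-2019 would be surveyed between 13-Jul-2019 (plus 42 days) and 10-Aug-2019 (plus 70 days).

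**4. How many women.** This needs two assumptions that the protocol does not make: even accrual over all 730 days, and a hard stop on 01-Jun-2019. For women recruited g days before delivery, the number who cannot reach week 6 is 200 × (42 + g) / 730.

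| Recruited | Calculation | Women | Share of 200 |
|---|---|---|---|
| At delivery (g = 0) | 200 × 42 / 730 | 11.5 | 5.8% |
| 4 weeks before (g = 28) | 200 × 70 / 730 | 19.2 | 9.6% |

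Week 6 is the right cut-off. One survey at any time from week 6 to week 10 satisfies F8, so a woman whose window is merely shortened has lost nothing if she is reached in time.

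**5. What that would cost.** The standard error of a correlation (Fisher scale) is proportional to 1/√(n − 3). Dropping from 200 to 188.5 women widens it by √(197/185.5) = 1.03, and dropping to 180.8 widens it by √(197/177.8) = 1.05. That is a loss of 3% to 5% in precision on secondary outcomes, before ordinary non-response.

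**6. The primary outcome.** Pain is recorded at 0 to 48 hours (F8), so the end date does not touch women who deliver before it. Only the most literal reading, with every woman recruited four weeks ahead, would place some deliveries after the end date: 200 × 28 / 730 = 7.7 women. Even then the standard error would grow by √(197/189.3) = 1.02.

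**The case for a change.** The best case for a change is that calling the dates estimates does not reconcile them: with a required survey six weeks or more after delivery, recruitment and study cannot both end on the same day. The form carries a submission date of 31-May-2018, a year before the end date, so there was time to align them. The correction would also be cheap: one or two dates, and one number in three places. The 6-10-week contact is moreover the point at which F8 refers women with high depression scores, so it is not merely an extra questionnaire.

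The inconsistency stands as a matter of record. The consequence does not. Nothing in the protocol stops surveys on 01-Jun-2019; that rule has to be supplied by the reader. It would also be an odd rule, since it would admit women in the final weeks whose own surgery could fall outside the study. A team that enrols a woman under a protocol with a 6-10-week survey will make that contact.

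The counts rest on even accrual to the last day, which is not stated. F3 reports 3000 to 4000 cesarean deliveries a year at the site. A target of 200 in two years is 100 a year, or 2.5% to 3.3% of that volume before eligibility and consent, so enrolment could well finish early. The document gives no accrual to date that would settle this.

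On the duration, 14 weeks is the sum of the listed windows without overlap, not a proven maximum. G3 and J1 allow consent at any time before labour, although J1 delays enrolment until the criteria are met. The protocol's wording is itself hedged, and the figure errs towards telling participants that they are involved longer than they are.

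**Conclusion.** No change to the plan follows. The shared end date is a gap that the study team fills in the obvious way, by completing follow-up for the last women delivered. The 17 weeks is a clerical slip of about 3 weeks in a descriptive figure that fixes no date, visit window, sample size or analysis.

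Under the least favourable reading (hard stop, even accrual, all women recruited four weeks ahead) about 19 of 200 would miss a secondary survey, and about 12 if they were recruited at delivery. These women would be left out because of the calendar date and not because of their pain, anxiety or depression scores, so the main cost is a few per cent of precision rather than an evident bias. If follow-up runs on, or enrolment fills early, the number is zero. No aim in F2 names a 6-10-week endpoint, and the primary correlation would be analysed and interpreted in the same way whichever dates are written.
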